5.4.1 Acupuncture Expectancy Scale

The validated ⁴⁷ Acupuncture Expectancy Scale consists of 4 items about subjects' expectations (e.g., my illness will improve a lot, my energy levels will increase) of the effects of acupuncture on a 5-point Likert-type scale from 1=*not at all agree* to 5=*completely agree*. Higher scores indicate greater expectations for the impact of acupuncture. Previous research suggests those who expect that acupuncture will be beneficial have better outcomes than those who are skeptical about the effect of acupuncture. This scale is appropriate only for those subjects randomized to the intervention acupuncture arm and will be performed only once- after Randomization but prior to the first acupuncture session.

5.4.2 Neuropathy 0-10

The primary outcome measure is subject-reported global ‘neuropathy’ right now, measured on an 11-point scale modeled after the Edmonton Symptom Assessment (ESAS) ⁷⁰ from 0=*no neuropathy* -10= *worst possible neuropathy*. This measure is of unknown validity, although it has been used in previously published studies on CIPN. ^{23,71} For clarity, subjects are provided with a definition of neuropathy with symptom descriptors.

5.4.3 Neuropathy Physical Location

Subjects will be asked about the physical location of their neuropathy, with options *hands/arms only*, *feet/legs only*, *both hands/arms and feet/legs*, *throughout the body*, and *other* with a write-in line. (This question is included on the Neuropathy 0-10 questionnaire)

5.4.4 FACT-GOG-NTX

The validated ⁵⁸ FACT-GOG-NTX questionnaire consists of 39 total items with a 7-day recall period on a 5-point Likert-type scale from 0=*not at all* to 5=*very much*. The questions address CIPN-specific symptoms (e.g., I have numbness or tingling in my hands, I have trouble buttoning buttons), physical well-being (e.g., I have a lack of energy), social/family well-being (e.g., I feel close to my friends), emotional well-being (e.g., I feel sad, I am satisfied with how I am coping with my illness), and functional well-being (e.g., I am able to work including work at home). This questionnaire has been previously used with myeloma patients. ⁶²

5.4.5 Other Symptoms

The FACT-GOG-NTX covers multiple symptoms of interest (i.e. nausea, sadness, nervousness, sleep quality, lack of energy, and general pain), however there are additional symptoms that will be examined in the current study. To avoid duplication and reduce respondent burden, only those symptoms not covered in the FACT-GOG NTX will be asked about separately. These are constipation, dizziness, and dry mouth. ⁷² These will be assessed with the same 7-day recall period on a 5-point Likert-type scale from 0=*not at all* to 5=*very much* as the FACT-GOG-NTX to make the symptoms comparable. This is a self-created measure of unknown validity.

5.4.6 CDC HRQOL-4

The CDC HRQOL-4 is a validated ^{45,46} four-item questionnaire used to measure health related quality of life (HRQOL). The first question asks about general health with response options *excellent*, *very good*, *good*, *fair*, and *poor*. The remaining three questions ask about the *number of days* in the past 30 days that the respondent was in poor physical health, poor mental health, and was unable to do their usual activities. This questionnaire has been used in the Behavioral Risk Factor Surveillance System (BRFSS) since 1993, the National Health and Nutrition Examination Survey (NHANES) from 2000-2012, and the Medicare Health Outcome Survey (HOS) since 2003. ⁷³

6. STUDY CALENDAR

Procedures/Assessments	Screening Visit	Baseline (complete within 2 weeks from consent, can be done at screening AFTER Randomization)	Weeks 1-2 ² : Twice per week	Weeks 3-10 ² : Once per week	Week 5 ± 1 week ^{3,5} Midpoint	Week 10 ± 1 week ^{3,5} Endpoint	Early Termination (if applicable) ⁷	Follow Up (30 days [+7] from last Acup tx)
Informed Consent Form	X							
Randomization via CTMS (within 2 weeks from consent)		X ¹²						
Sociodemographics & Medical History (see 5.3.1 and 5.3.2)		X						
Multiple Myeloma status ⁶		X						
ECOG	X							
Height / Weight/ BMI		X						
Acupuncture Expectancy Scale ⁴		X ⁴						
Acupuncture Treatment ^{1,2}			X ²	X ²				
Collect Chemotherapy regimen information ¹⁰	X					X	X	
Adverse Events of Special Interest ⁸			Continuously, starting at First Acupuncture session			X	X ¹³	
CIPN: Neuropathy 0-10 & neuropathy physical location	X ¹¹				X	X	X	
CIPN: FACT-GOG-NTX		X ¹⁴			X	X	X	
Other Symptoms: Constipation, dizziness, dry mouth		X ¹⁴			X	X	X	
Quality of Life: CDC HRQOL-4		X ¹⁴			X	X	X	
Opioid Intake/ Morphine Equivalent Daily Dose (see Appendix B)		X ⁹			X	X	X	
Concomitant Medication: (See Section 5.3.4 for which medications to collect)		X ⁹			X	X	X	

Key to Footnotes

¹ First acupuncture session to occur within 2 weeks of enrollment (date randomized). Acupuncture treatment schedule to start on a Monday or Thursday only.

² Week 1 for subjects on the acupuncture/intervention arm is the week when the first acupuncture session occurs. Window for acupuncture sessions during Week 1 and Week 2 is at least 1 day (minimum) and no more than 8 days (maximum) between visits. Window for sessions during Weeks 3-10 is at least 2 days (minimum) and no more than 9 days (maximum) between visits. During Week 1 and Week 2, if an acupuncture session is missed, it may be made up the following week (there will be 3 sessions that following week). During Weeks 3-10, no sessions will be made up if missed.

³ Questionnaires at Midpoint and Endpoint should still be collected even if subject decides to discontinue the acupuncture sessions but is willing to stay on study. Week 1 for the control group begins at Randomization.

⁴ Acupuncture Expectancy Scale questionnaire to be collected only from subjects on Intervention (Acupuncture) arm at any time AFTER Randomization has occurred, but PRIOR to first acupuncture session.

⁵ For acupuncture arm, Midpoint occurs at Week 5 ± 1 week from first acupuncture session, with Endpoint occurring at Week 10 ± 1 week from first acupuncture session. For control arm, Midpoint occurs at Week 5 ± 1 week from Randomization with Endpoint occurring at Week 10 ± 1 week from Randomization.

⁶ Collect MM date of diagnosis and staging at Baseline

⁷ If a subject decides or needs to be withdrawn from the study early (all visits and acupuncture assessments, if applicable), but is willing to complete an Early Termination visit, subject will complete assessments a final time, and will be considered Off Study (See section 8.2). Subjects do not need to complete questionnaires if they have done so within the last 2 weeks.

⁸ AESIs should only be collected on subjects randomized to acupuncture arm, beginning with first acupuncture session until 30 days after final acupuncture session.

⁹ For collection of opioid medication intake and concomitant medications, collect what has been taken over the past 7 days.

¹⁰ Collect chemotherapy regimen information throughout the study (if applicable).

¹¹ CIPN Neuropathy 0-10 & neuropathy physical location questionnaire is to be completed the first time **after consenting and prior to any other baseline procedures or assessments** to determine if the subject qualifies for enrollment into the study (see section 7.1.1).

¹² Notify subject of their randomization result.

¹³ Follow Up on AESIs: Can be done over the phone- this follow up for AESIs is only for subjects randomized to Acupuncture treatment arm.

¹⁴ Questionnaire may be completed after consent and prior to or after Randomization

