7.1.2 Midpoint and Endpoint visits

The following assessments and questionnaires will be repeated at the Midpoint visit (Week 5 ± 1 week) and at the Endpoint visit (Week 10 ± 1 week) from randomization for the control arm. The assessments and questionnaires will be completed for the acupuncture arm at Midpoint visit (Week 5 ± 1 week) and Endpoint (Week 10 ± 1 week) from first acupuncture session. The questionnaires (see section 5.4) will be administered either in the clinic or via electronic survey or certified mail. The questionnaires should be completed with subjects in both arms, and regardless of whether the intervention (acupuncture) was received. Subjects in both arms will complete the study questionnaires at protocol defined timepoints, even if bortezomib/bortezomib-combination therapy is removed from their treatment regimen during the study (for those on active bortezomib treatment).

Note: These same assessments and questionnaires will be performed if the subject has an Early Termination visit (see study calendar).

See section 5.4 for more detailed information on the study questionnaires.

- Collect AESI information, if applicable (for those on acupuncture arm)
- Collect chemotherapy regimen information.
- CIPN: Neuropathy 0-10
- CIPN: Neuropathy physical location
- CIPN: FACT-GOG-NTX
- Other symptoms (constipation, dizziness, dry mouth)
- CDC HRQOL-4
- Morphine Equivalent Daily Dose (Past 7-day recall)
- Concomitant medication intake (Past 7-day recall)

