8. REMOVAL OF SUBJECTS FROM STUDY

8.1 Off Treatment

If subjects on the acupuncture arm decide to discontinue the acupuncture sessions but continue the questionnaires and other assessments, they will be considered Off Treatment. Reasons for coming off treatment would include, but not be limited to:

- Completed protocol therapy
- Adverse event (toxicity)
- Non-compliance
- Investigator decision
- Consent withdrawal for acupuncture sessions
- Subject death
- Study closure

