8.2 Off Study

Once all on-study assessments and procedures are completed, subject will be considered Off Study. Subjects on the acupuncture arm will be followed for AESIs for 30 days post the last acupuncture session, then they will be Off Study.

Subjects may stop their participation in this study at any time if they no longer wish to participate, or if the investigator believes this to be in the best interest of the subject.

When subjects are removed from the study, the reason for study removal and date the subject was removed should be documented. Reasons a subject may be removed from study include, but are not limited to:

- Subject non-compliance with study participation, in the opinion of the investigator
- The subject withdraws study consent
- The subject is lost to follow-up
- Investigator's decision to withdraw the subject

- Subject death

Subjects that are Off Study will not participate in any study related procedures, including data collection.

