10. POTENTIAL RISKS/UNANTICIPATED PROBLEMS

10.1 Adverse Events of Special Interest

Adverse Events of Special Interest will be collected only for those subjects on the intervention arm, beginning with start of first acupuncture session. AESIs will be collected through 30 days post last acupuncture session. Subjects who experience an AESI will be medically managed by their physician or acupuncturist through standard of care, as appropriate. These events should only be captured if deemed **related** to the acupuncture intervention per the Investigator.

All AESIs will be graded per CTCAE 5.0.

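### The protocol gives two different times at which an acupuncture subject who leaves early becomes Off Study, and one of them ends AESI collection before the 30-day window closes

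*Combined protocol and SAP*

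**What the plan says.** Two sets of statements bear on an acupuncture-arm subject who leaves early.

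**Collection stops at Early Termination.** Footnote 7 of the study calendar (section 6) covers a subject who chooses, or has, to be withdrawn from the whole study but will attend one last visit: "subject will complete assessments a final time, and will be considered Off Study (See section 8.2"). The last line of section 8.2 adds: "Subjects that are Off Study will not participate in any study related procedures, including data collection".

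**Collection runs for 30 days.** Footnote 8 sets the AESI period as "beginning with first acupuncture session until 30 days after final acupuncture session". Section 10.1 agrees: "AESIs will be collected through 30 days post last acupuncture session". The calendar has a Follow Up column at 30 (+7) days from the last session, and footnote 13 describes it: "Follow Up on AESIs: Can be done over the phone- this follow up for AESIs is only for subjects randomized to Acupuncture treatment arm". Section 8.2 opens with: "Subjects on the acupuncture arm will be followed for AESIs for 30 days post the last acupuncture session, then they will be Off Study". None of these makes an exception for early leavers.

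Two further provisions limit the problem. Section 7.1.2, whose list includes AESI information, says: "These same assessments and questionnaires will be performed if the subject has an Early Termination visit (see study calendar"). Section 8.1 deals separately with subjects who "decide to discontinue the acupuncture sessions but continue the questionnaires and other assessments, they will be considered Off Treatment", and it lists adverse event among the reasons.

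**The concern.** Sections 11.3.3 and 11.5.6 make the AESI proportions in the acupuncture arm, with Clopper-Pearson 95% intervals, the trial's only defined safety endpoint. Such a proportion is easy to interpret when every subject is observed over the same window after the last session. If some subjects are closed out at Early Termination and the rest are followed for 30 days, the denominator mixes unequal windows, and a first event in the unobserved part goes uncounted.

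Footnote 7 is the text written specifically for early leavers, so a coordinator could reasonably act on it. Once an Off Study date is entered, the last line of section 8.2 forbids the later call. Another coordinator, reading the opening of section 8.2, would make the call. The same situation could therefore be handled differently from one subject to the next.

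**Working it through.** The plan gives no figure for AESI follow-up in early leavers. The check is mainly a comparison of text, followed by simple arithmetic on what is exposed.

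**1. Who is affected**

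| Situation | Governing text | AESI follow-up |
|---|---|---|
| Completes all sessions | Opening of 8.2; footnote 8; 10.1 | Full 30 days |
| Stops sessions, continues assessments | 8.1 (Off Treatment); calendar footnote 3 | Full 30 days |
| Leaves the study, attends Early Termination | Footnote 7 with last line of 8.2, **or** opening of 8.2 with footnote 8 and 10.1 | Ends at the visit, **or** 30 days |
| Withdraws consent to all contact | 8.2 | Not possible under any wording |

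Only the third row is in conflict.

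**2. How much of the window is exposed.** AESIs up to the visit are collected at the visit (7.1.2). If the visit is d days after the last session, the literal footnote 7 reading loses 30 − d days. The documents do not fix d, so it is varied as an assumption:

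| d (days) | Days lost | Share of window |
|---|---|---|
| 0 | 30 | 100% |
| 7 | 23 | 77% |
| 14 | 16 | 53% |
| 21 | 9 | 30% |
| 30 | 0 | 0% |

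**3. What could be missed.** Section 11.3.3 defines each AESI as a yes/no variable per subject. An event already recorded at the visit stays counted whatever happens later. Only a new event, or one that first reaches its grade threshold (10.1.1, 10.1.2) after the visit, can be lost.

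**4. How many subjects.** Section 11.2 plans 75 enrolled for 66 evaluable. The implied loss is (75 − 66)/75 = 12%, and 66/(1 − 0.12) = 75, so the two figures agree.
- Non-evaluable: 75 − 66 = 9.
- On acupuncture at 2:1 with equal loss by arm: 9 × 2/3 = 6, out of 75 × 2/3 = 50.
- 6/50 = 12%.

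This is a ceiling under its assumptions, because it treats every non-evaluable subject as leaving through Early Termination. Non-evaluable in section 11.4 means lacking a complete baseline or Week 10 neuropathy score, which also covers missed questionnaires, deaths and loss to follow-up. If loss were unequal and all 9 fell in the acupuncture arm, the figure would be 9/50 = 18%.

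**5. What one missed event does.** With n = 50, the two-sided 95% Clopper-Pearson upper limit is:
- 0/50: 1 − 0.025^(1/50) = 7.1%.
- 1/50: the 97.5th percentile of Beta(2, 49) = 10.6%.

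This shows how sensitive the interval is to one event. It does not show that this rule would cause one to be missed.

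**The case against.** The strongest reply is that the documents already contain the answer. Footnote 7 refers the reader to section 8.2, and section 8.2 has a rule specific to the acupuncture arm that places Off Study after the 30 days. Footnotes 8 and 13, the Follow Up column and section 10.1 all point the same way. Footnote 7 can then be read as ending visits and questionnaires only. This stands to the extent that loss of follow-up is one of two readings and is not a settled outcome. It does not remove the conflict, because footnote 7 ties Off Study to the final assessments and the last line of section 8.2 has no AESI exception.

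A reader might also infer that follow-up is lost selectively in subjects who left because of harm. The documents do not support that. Adverse event is listed under Off Treatment in section 8.1, where assessments continue, and is not among the Off Study reasons in section 8.2. The section 8.2 list is open-ended and allows removal in the subject's best interest, so leaving the study because of harm is possible. No reasons or rates are given.

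A reader might further infer bias from events that worsen after the visit. That fails because the endpoint is yes/no per subject: a needling-site infection recorded at Early Termination remains counted however it develops.

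Finally, safety information is not confined to AESIs. Disposition reports deaths and treatment discontinuations with reasons (11.5.2), and unanticipated problems are reported to the IRB (10.4.2). That is correct, but it does not supply AESI data for the missing days.

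**Conclusion.** The conflict holds as an internal inconsistency. Read literally, footnote 7 and the last line of section 8.2 end AESI collection at Early Termination, while footnote 8, section 10.1, the Follow Up column and the opening of section 8.2 continue it to 30 days after the last session. If a site follows footnote 7, the AESI proportions may be understated through first events in the remaining days. A definite loss, a loss concentrated in harmed subjects, and a demonstrated downward bias are not established.

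The size is small. The ceiling of about 6 of 50 subjects rests on equal loss by arm and on every non-evaluable subject leaving through Early Termination, and the true number could be near zero. The days exposed depend on an assumed visit date. Sample size, significance level and power are unaffected. The inconsistency should be corrected because it concerns the only defined safety endpoint and the correction is cheap.

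**What to change.** Amend footnote 7 and section 8.2 together. Early Termination would end sessions, visits and questionnaires. An acupuncture-arm subject would become Off Study only after the 30-day (+7) AESI contact already in the calendar, which footnote 13 allows by phone, unless the subject withdraws consent to further contact. The last line of section 8.2 can then stand, since it would apply only after that contact. Control subjects would still become Off Study at Early Termination.

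This gives the acupuncture arm one AESI window for the reported proportions, apart from subjects who refuse contact or cannot be reached. Recording the later outcome of AESIs still open at the contact is not needed, because no stated endpoint uses it.

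The cost is about one sentence in each place, one phone call for a small number of subjects, and Off Study dates up to about a month later for them.

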1.2 Study Rationale and Study Design

This randomized, controlled trial (see Schema) is designed to evaluate the effect of acupuncture on CIPN, other symptoms, and potential opioid and concomitant medication sparing effects in comparison to standard of care management in MM subjects. We hypothesize that acupuncture will be associated with: 1) a clinically significant and statistically significant reduction in CIPN; 2) statistically significant reduction of other symptoms such as nervousness and lack of energy; and 3) statistically significantly improved QOL at ten weeks. We also theorize that acupuncture will be opioid and concomitant medication sparing at ten weeks. We expect that the dose of acupuncture received will impact the outcomes, with higher doses of acupuncture being associated with better outcomes.

This study is novel in that it will be, to our knowledge, 1) the largest randomized, controlled trial to examine the effect of acupuncture on CIPN in MM patients 2) the first to explore the impact of acupuncture on opioid and concomitant medication intake.

This project aims to strengthen the care of persons with MM by improving quality of life (QOL) and ability to perform daily activities through reduced CIPN symptoms. CIPN debilitates and erodes QOL by preventing individuals from pursuing their normal activities of daily living. The features of CIPN, including physical, social/family, emotional, functional, and specific CIPN

symptoms, will be measured with the validated FACT-GOG-NTX.⁵⁸ This project brings necessary attention and scientific inquiry to supportive cancer care, which is sometimes de-prioritized behind disease treatment.^{59,60} The potential for nonpharmacologic acupuncture to reduce CIPN and other symptoms with minimal side effects has beneficial implications for disease treatment. Patients with controlled symptoms are better able to tolerate life-prolonging treatment and avoid chemotherapy dose reductions which result from neurotoxic side effects of chemotherapy.^{11,61,62}

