4. SUBJECT ALLOCATION

4.1 Randomization

Subjects will be randomized in a 2:1 fashion to either acupuncture plus standard subject management or standard of care alone and assigned a Sequence Number. This will be accomplished utilizing the CTMS, whereby a list of Sequence Numbers and associated treatment arm assignments randomly generated prior to study activation will be uploaded by a member of the Levine Cancer Institute Biostatistics Core. The Sequence Number will be a four digit, randomly generated ID number, ranging from 0001 to 9999. A stratified block randomization will be utilized including the following stratification factors to reduce confounding of comparisons between the treatment arms:

- Baseline neuropathy score (neuropathy score 2 – 6 vs 7 – 10)

Blinding will not be possible within this trial because the subjects and study personnel will be able to decipher intervention from control based on the study activities. Those exposed to acupuncture will understand that they are in the intervention group and those given standard of care only will understand that they are in the control group. If a subject in the control group has an acupuncture session while enrolled, they will be discontinued from the study and all further assessments at that point.

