7. ADDITIONAL INFORMATION ON STUDY PROCEDURES

7.1.1 Screening/Baseline

Subjects will be consented to the trial, and the CIPN Neuropathy 0-10 (and physical location) questionnaire will be administered. Subjects who score <2 on the CIPN Neuropathy 0-10 questionnaire will be a screen failure and will not be randomized or enrolled into the study. If CIPN Neuropathy 0-10 is answered sufficiently for inclusion (score ≥ 2), the rest of the baseline assessments are to be completed within two weeks from consent. Once eligibility is confirmed, subject will be randomized via CTMS to either Acupuncture (intervention arm) or Standard of Care. Subjects will be notified of their randomization result. Those randomized to Intervention Arm will begin acupuncture sessions within two weeks of enrollment.

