11.5.4 Primary Analysis

The frequency and proportion of subjects who experienced at least a 2-point improvement in neuropathy between the baseline score and the score obtained at Week 10 (+/- 1 week) will be calculated for each study arm. A two-sided Fisher Exact test will be executed, testing the null hypothesis that there is no difference in neuropathy improvement rate between the arms.

Additionally, logistic regression will be used to evaluate the impact of acupuncture while adjusting for potential baseline confounding factors, including the stratification variable, baseline neuropathy severity grade. Univariate models will be used to identify baseline factors that are individually prognostic. Statistically significant factors identified from the univariate models will then be included in a multivariable model. Backward elimination will be used to identify baseline factors that are independently prognostic. A treatment indicator variable will be added to obtain an adjusted odds ratio.

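### The baseline FACT-GOG-NTX, other-symptom and HRQOL-4 questionnaires may be answered after subjects in this unblinded trial have learned their arm

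*Combined protocol and SAP*

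**What the plan says.** In section 6 (Study Calendar), footnote 14 is attached to the Baseline cell of three rows: FACT-GOG-NTX, other symptoms (constipation, dizziness, dry mouth) and CDC HRQOL-4. It reads "Questionnaire may be completed after consent and prior to or after Randomization". The Baseline column header gives a similar permission for the whole column: "can be done at screening AFTER Randomization".

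Footnote 12, on the randomization row, is "Notify subject of their randomization result", and section 7.1.1 repeats it. Section 4.1 states "Blinding will not be possible within this trial because the subjects and study personnel will be able to decipher intervention from control".

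Section 7.1.1 mentions the remaining baseline assessments before it mentions randomization, but the only limit it sets is that "the rest of the baseline assessments are to be completed within two weeks from consent".

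Two other measures do have a fixed position. Footnote 11 puts the Neuropathy 0-10 score straight after consent and ahead of every other baseline procedure. Footnote 4 puts the Acupuncture Expectancy Scale, in the acupuncture arm only, between randomization and the first session.

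**The concern.** A baseline value is useful in a randomized comparison because allocation cannot have influenced it. Here the three instruments are self-reports, the subject may already know the arm, and nothing requires the questionnaire to come before notification. The protocol itself treats expectation as relevant to self-reported results. Section 5.4.1 says that "those who expect that acupuncture will be beneficial have better outcomes than those who are skeptical". A subject who has just learned of assignment to acupuncture, or to standard care alone, might rate symptoms differently from one who does not yet know. The direction cannot be predicted.

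If such a shift occurs, subtracting or adjusting for the affected baseline transfers it into the treatment comparison. A baseline table built from these scores could also show an imbalance caused by knowledge of the arm, or hide one due to chance.

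**Working it through.** **Which endpoints draw on these instruments (section 11.3.2).** NTX subscale, nausea, sadness, nervousness, sleep, energy and pain: 7. Constipation, dizziness and dry mouth: 3. General health, unhealthy days and activity limitation days: 3. Total 7 + 3 + 3 = 13, which is every secondary endpoint. Ten are 5-level ordinal items (six FACT items, three added symptoms, general health). The other three are the NTX sum and two day counts.

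**What is not affected.** The primary endpoint uses the Neuropathy 0-10 score, which is taken before randomization because it decides eligibility. The stated power (at least 80% for 0.10 versus 0.35, 22 and 44 subjects, two-sided alpha 0.20) uses none of the three instruments. Exact enumeration of the two-sided Fisher test gives 81.7%, so that figure reproduces and would not change.

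**Where these baselines could enter an analysis.**
- Section 11.5.5 plans analysis of variance, on ranks for the ordinal items, and does not say whether baseline is used.
- Section 1.2 hypothesises a "statistically significant reduction of other symptoms such as nervousness and lack of energy" and better quality of life, which reads as change but is rationale rather than an analysis rule.
- Section 11.5.4 says "logistic regression will be used to evaluate the impact of acupuncture while adjusting for potential baseline confounding factors". It names the stratification variable and gives no list of other candidates.
- Section 11.5.5 lets the same factors into the repeated-measures model for the binary neuropathy response.

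**Illustration on assumed inputs.** The documents give no shift or correlation, so both are assumptions. Take no true effect, normal data with unit SD at baseline and Week 10, correlation r, an average baseline shift of d SD in one arm, n = 22 and 44, and a nominal two-sided 5% test.

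Standard error factor: sqrt(1/22 + 1/44) = 0.261.

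- Change score: bias d, SD sqrt(2(1 - r)), noncentrality d / (0.261 × sqrt(2(1 - r))), 64 df.
- Baseline-adjusted: bias r × d, SD sqrt(1 - r²), noncentrality r × d / (0.261 × sqrt(1 - r²)), 63 df.
- Week 10 values alone: bias 0, so 5%.

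For d = 0.2 (the whole arm answers after notification and shifts by 0.2 SD):

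| r | Change: noncentrality | Change: rejection | Adjusted: noncentrality | Adjusted: rejection |
|---|---|---|---|---|
| 0.5 | 0.2 / (0.261 × 1.000) = 0.766 | 11.7% | 0.10 / (0.261 × 0.866) = 0.442 | 7.2% |
| 0.7 | 0.2 / (0.261 × 0.775) = 0.989 | 16.4% | 0.14 / (0.261 × 0.714) = 0.751 | 11.46% |

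If only half of that arm is shifted, the average shift is 0.5 × 0.2 = 0.1 SD:

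| r | Change: rejection | Adjusted: rejection |
|---|---|---|
| 0.5 | 6.6% | 5.5% |
| 0.7 | 7.8% | 6.6% |

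A simulation of 20,000 runs at d = 0.2 agrees. For r = 0.5 it gives 5.2% (Week 10 alone), 11.4% (change) and 7.4% (adjusted); for r = 0.7 it gives 4.8%, 16.4% and 11.3%. With d = 0 every method stays at 5%.

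**The case against.** The strongest reply is that no documented analysis uses these baselines. Section 11.3.2 defines the secondary endpoints as score levels, and section 11.5.5 tests them by arm with no baseline term. Where the plan wants a change from baseline it says so, as it does for the primary endpoint. On that reading the secondary tests compare later scores and this issue does not reach them. The reply is fair, and it is why the harm is only conditional. It does not close the point, because the plan never commits to Week 10 values alone and collects all three instruments at baseline.

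The covariate route is also open rather than planned. Section 11.5.4 names only the stratification variable, and section 11.5.3 speaks of demographics and selected medical history. No passage names FACT-GOG-NTX or HRQOL-4 scores as candidates. They are not excluded, and no more than that can be said.

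The illustration has limits that stand. It uses normal-theory tests although ten of the 13 endpoints are 5-level ordinals and two are bounded day counts. The shift has no support in the documents: the items ask about the past 7 or 30 days, and section 5.4.1 links expectation to outcome, not to recalled baseline symptoms. Answering late is optional, so a shift in every subject of one arm is an extreme case.

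A reader might infer that section 7.1.1 already requires these questionnaires before randomization. It describes that order but sets only the two-week limit, so it does not override footnote 14. A reader might also infer that these baselines could follow the first acupuncture session. No sentence expressly forbids it, but the calendar places Baseline ahead of Weeks 1-2 and section 7.1.1 mentions acupuncture last, so the point does not rest on that.

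**Conclusion.** The point holds as a weakness in a stated rule. The plan allows the baseline self-reports behind 13 of 13 secondary endpoints to be given with knowledge of the arm. That count describes what is permitted; it does not show that 13 comparisons are biased. Bias follows only if subjects answer after notification, if knowing the arm changes their answers, and if the analysis or baseline table uses the scores. Its direction is unknown.

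The rates of about 12-16% (change score) and 7-11% (baseline-adjusted) at a nominal 5% are a worst case on assumed inputs. With half the arm shifted they are about 7-8% and 6-7%.

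A reader might infer that the primary result is compromised or that the secondary error rates are already inflated. The documents support neither. The primary baseline precedes randomization, the unadjusted Fisher test and the sample size do not use these instruments, and the plan fixes no use of the affected scores. The timing permission itself is clear from the text. This is an inexpensive improvement worth considering.

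**What to change.** 1. Amend footnote 14 so that FACT-GOG-NTX, other symptoms and CDC HRQOL-4 are completed after consent and after the Neuropathy 0-10, and before randomization, or at the latest before the subject is notified of the arm. Keep the existing two-week window. Exempt these three from the permission in the Baseline column header. Leave the Acupuncture Expectancy Scale as footnote 4 has it.
2. Record for each questionnaire whether it was completed before or after notification. A date alone may not show this, because screening, randomization and the questionnaires can fall on the same day. Where completion came after notification, or the order cannot be established, report the number by arm and do not use those scores as covariates or in change scores.

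Cost: no new instrument or visit, one extra item on the case report form, and a slightly longer step before randomization. Because sections 5.1 and 5.4 allow certified mail and electronic survey, randomization may sometimes have to wait for a returned questionnaire within the two weeks.
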